### **13.7.1.2 Primary Analysis**

#### **13.7.1.2.1 Handling of Dropouts or Missing Data**

All randomized participants will be included in the primary ITT efficacy analysis. Participants not reaching the primary efficacy endpoint by the study end date, or before their last assessment for participants lost to follow-up, will be censored at the date of their last assessment visit.

#### **13.7.1.2.2 Data Transformation Before Analysis, If Any**

No data transformation will be applied to raw data.

#### **13.7.1.2.3 Main Statistical Model and Adjustment for Covariates**

For the primary analysis, all adjudicated events occurring from randomization to the study end date (inclusive) will be counted, including events occurring after early permanent discontinuation of study medical device. The proportion of participants remaining event-free over time will be displayed in the form of survival curves using the Kaplan-Meier method and analyzed (primary analysis) using a two-sided log-rank test. Statistical significance will be claimed if the computed p-value is equal to or less than 0.05.

The number and percentage (crude rate) of participants experiencing a primary endpoint will be summarized.

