**CLINICAL TRIAL PROTOCOL**  
**(Phase IV - Efficacy Trial)**

**Medical Device: FDA K031876 ELECTRO FLO PERCUSSOR, MODEL 5000**

**Non-randomized, multisite site, single arm study for the efficacy of current FDA 510k indication for adults between the ages of 18 and 55 (non-smokers).**

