# **6. STUDY DESIGN**

## **6.1 Description of the Protocol**

The present study is designed as a multi-center, non-randomized, single-blind, one arm group trial with 70 participants per arm.

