### **8.3 Method of Assigning Participants to Treatment Group**

N/A - All included shall be assigned to the single arm.

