#### **13.7.1.2.4 Multiple Comparisons/Multiplicity**

If the primary efficacy reaches statistical significance, then the two secondary endpoints will be formally tested at the 5% level in a hierarchical (step-down) procedure.

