#### **13.7.1.2.5 Other Analyses for Primary Variable(s)**

In order to further investigate the primary endpoint the following analysis will be done:

**Subgroup Analysis:** The incidence of the primary efficacy endpoint will be summarized by a number of covariates including age, gender, and race to examine their potential effects. Each of these factors will be analyzed statistically using a Cox proportional hazards model incorporating terms for treatment, the covariate and the treatment-by covariate interaction. The number of participants with outcomes, estimated hazard ratios, and associated 95% confidence intervals will be calculated within each of the subgroups generated by these analyses.

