#### **13.7.2.2 Statistical Analysis of Secondary/Other Variables**

The secondary and other endpoints will be analyzed using the same statistical methodology as for the primary efficacy endpoint (except for weight and waist circumference).

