## 2. Study Sponsor responsibilities

The Study is being sponsored by Med Systems, Inc., LTD., and monitored by Med Systems, Inc., LTD.. As such, they will share legal and regulatory responsibilities for the conduct of the study and control and distribution of the investigational device, Electro Flo 5000 . In fulfilling these responsibilities according to Med Systems, Inc., LTD. standard operating procedures, the Sponsor's activities include the following:

- Medical Input
  - Participate at the Operations Committee and the Executive Committee meetings or teleconferences
  - Update the Clinical Investigator's Brochure at least annually
- Medical Device Supplies
  - Manufacture and ship medical devices and matching-placebos
  - Release medical device supplies to individual Clinical Centers after receipt of documentation at the Sponsor's regional centers
- Funding
  - Provide indemnification letters as required
  - Provide funding and contracting with Investigators for the conduct of the study.
- Regulatory
  - Obtain all necessary documents from Investigators for regulatory filings

- Ensure initial, and then annual (when applicable) IRB/EC approval is obtained by Investigators
- Monitor compliance with all applicable national and local law maintain and coordinate contact with national regulatory authorities
- Submit all necessary regulatory filings oversee all communication between DMC and regulatory authorities to make certain it occurs in a timely manner
- Perform all statistical analysis and medical writing of clinical reports for
- Registration applications
- Study Monitoring
  - Develop a study monitoring plan
  - Monitor clinical centers
  - Ensure protocol adherence
  - Assess timely completion and submission of Case Report Forms (CRFs) and support documents
  - Monitor quality and homogeneity of all data processing activities
  - Quality Assurance audits of the study as needed
  - Monitoring and overseeing the maintenance of study conduct according to ICH, GCPs, and all country-specific regulations
  - Clarify queries or missing documents, including assisting Optional Study Group Project Team to
  - Clarify queries or missing documents from US sites maintain necessary communication with all National Coordinators, Investigators and study personnel
- Data Management and Study Medical device Allocation Procedure

- Develop and manage the Central Study Database, perform data entry and validate records in the email acquisition system

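### The primary success rule is a log-rank p-value, but a single-arm trial with no reference value cannot produce one, so the gate to the secondary endpoints can never open

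*Protocol*

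**What the plan says.** The design is stated consistently in three places. The protocol title reads "Non-randomized, multisite site, single arm study for the efficacy of current FDA 510k indication". Section 6.1 describes a "one arm group trial with 70 participants per arm". Section 8.3 says "All included shall be assigned to the single arm". Section 4.3 adds that a placebo control is not needed because each participant is compared before and after treatment.

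The confirmatory analysis belongs to a different design. Section 13.7.1.1 defines the primary efficacy endpoint as time to a first adjudicated event (skin condition, allergic reaction or new medical condition). Section 13.7.1.2.3 says that this will be "analyzed (primary analysis) using a two-sided log-rank test. Statistical significance will be claimed if the computed p-value is equal to or less than 0.05". Three further provisions depend on that rule:

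- Section 13.7.1.2.4: "If the primary efficacy reaches statistical significance, then the two secondary endpoints will be formally tested at the 5% level".
- Section 13.7.2.2: the secondary endpoints are "analyzed using the same statistical methodology as for the primary efficacy endpoint".
- Section 13.7.1.2.5: subgroups use a "Cox proportional hazards model incorporating terms for treatment, the covariate and the treatment-by covariate interaction".

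The SAP sets a general two-sided 5% level and asks for 95% confidence intervals in summaries of continuous variables. It names no primary test and no reference value.

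**The concern.** A log-rank test compares two or more survival curves, or, in its one-sample form, one curve with a stated reference. This trial has one curve and no reference. If no p-value can be computed, the only rule for claiming success is empty. The hierarchical step to the secondary endpoints then never starts, and those endpoints would fail in the same way on their own.

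Meanwhile the outcomes in the objectives, percentage change in SpO2 (5.1) and in FVC and FEV1 (5.2), have no named confirmatory test. Someone would have to choose the real primary analysis later. In a one-arm study whose data for both objectives go to the investigator by day (8.11), that choice could be made with the results in view.

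**Working it through.** **Inputs.** One arm, N = 70 (6.1, 8.3); two-sided log-rank test, success at p ≤ 0.05 (13.7.1.2.3); withdrawals not replaced (11.2). No event rate, reference curve, performance goal, SD, power or dropout rate is given. Sections 7.1 and 13.2 refer to event rates without a number, and 9.1.1.1 names a composite rate of success without a threshold. The plan's own figure of 70 therefore cannot be reproduced from its inputs.

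**The stated test.** At an event time with n at risk, n₁ of them in group 1, and one event, the expected count is n₁/n and the variance is (n₁/n)(1 − n₁/n). With one group n₁ = n, so each event adds 1 to O, 1 to E and 0 to V. Direct computation for 70 participants with 5, 20 and 40 simulated events gave O − E = 0 and V = 0 each time. The statistic (O − E)²/V is 0/0 with zero degrees of freedom, whatever the data.

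**The Cox model.** Treatment is constant and treatment × covariate equals the covariate. For treatment, age and their interaction, the centred design has rank 1 of 3. Only the covariate effect can be estimated.

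**A one-sample log-rank test.** Suppose 7 events in 70 (illustrative) and an assumed reference event-free proportion S₀. Let L = −ln S₀. Counting a full L for each of the 63 event-free participants and half for each of the 7 with events, E = 63L + 3.5L = 66.5L and Z = (7 − E)/√E.

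| Assumed S₀ | E | Z | two-sided p |
|---|---|---|---|
| 95% | 3.41 | 1.94 | 0.052 (worse than reference) |
| 90% | 7.01 | 0.00 | 0.998 |
| 85% | 10.81 | −1.16 | 0.247 |
| 80% | 14.84 | −2.03 | 0.042 |
| 75% | 19.13 | −2.77 | 0.006 |

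The same data give almost any answer, so the reference has to be fixed in advance.

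**An exact one-sample test of the event-free proportion** (N = 70, one-sided 0.025, assumed goals). A 75% goal allows at most 10 events (power 0.913 if the true proportion is 90%), an 80% goal at most 7 (0.599), and an 85% goal at most 4 (0.159).

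**A paired test of percentage change**, one value per participant, two-sided 5%. The detectable difference d, in SDs of that value, solves P(|T| > t₀.₉₇₅) = power, where T is noncentral t with n − 1 degrees of freedom and noncentrality d√n. The 95% CI half-width is t₀.₉₇₅/√n.

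| n | d, 80% power | d, 90% power | half-width |
|---|---|---|---|
| 70 | 0.340 | 0.393 | 1.995/√70 = 0.238 |
| 63 (assumed 10% loss, 70 × 0.9) | 0.359 | 0.415 | 1.999/√63 = 0.252 |

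If there is truly no change, a two-sided rule with no stated direction succeeds 5.0% of the time. Requiring improvement as well makes this 2.5%, with the same d to four decimals.

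**Zero-change imputation as a sensitivity analysis.** Adding 7 zeros to 63 pairs moves t from 2.000 (p = 0.0499) to 1.995 (p = 0.0500). Adding 35 zeros to 35 pairs moves p from 0.0174 to 0.0186. The mean and its standard error shrink together, so this does not test robustness to missing data.

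**The case against.** *Other text implies a second group.* Appendix 1 has the sponsor "Manufacture and ship medical devices and matching-placebos" and run a central randomization system, and Appendix 5 describes double-blinding. A reader might infer a control arm that the log-rank test was meant to use. The documents do not support that: the title and sections 4.3, 6.1 and 8.3 are explicit, and the appendices define no comparator, allocation or control sample size.

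*A paired test is implied.* This is the strongest objection, and part of it stands. Section 4.3 does declare a before/after comparison, and the SAP's 95% confidence intervals arguably already cover mean change. It would be wrong to say that the plan contains no comparison. But no section names a paired test as confirmatory, and section 13.7 ties the p-value rule and the gate to the log-rank test alone.

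*A one-sample log-rank test was meant.* It needs a reference that the documents lack.

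*The plan can be revised before data lock (13.1).* That safeguard is blinded review, and with one arm there is no allocation to conceal.

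*The looks at Days 7, 14 and 21.* A reader might infer uncontrolled interim efficacy testing. Section 6.3 gives them a safety purpose, and section 6.4 says that DMC review of efficacy data is not a formal interim analysis. The documents do not support an inflation claim; the looks bear on when the analysis must be fixed.

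**Conclusion.** The primary analysis is wrong as written and must be fixed. The stated test has no power in any useful sense because no statistic exists. The gate in 13.7.1.2.4 cannot open, 13.7.2.2 passes the same failure to the secondary endpoints, and the treatment and interaction terms in 13.7.1.2.5 cannot be estimated. This rests only on there being one arm and no reference value, and both follow from the text.

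A reader might go further and infer that nothing can be analysed. That does not follow: Kaplan-Meier curves, crude rates, covariate-only models and confidence intervals all remain available. What is missing is a confirmatory conclusion.

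The repair figures are in SD units because the documents give no SD. The 10% loss, the 7 events and the reference proportions are assumptions. The choice of endpoint belongs to the sponsor; the defect does not dictate it.

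**What to change.** Settle the following before any outcome data are reviewed. Because data go to the investigator by day (8.11), that means before the first participant's data, not merely before Day 7.

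1. **Endpoint.** Name one primary endpoint, one post-treatment time and one pre-treatment reading, reconciling 5.1, 9.1, 9.1.1, 9.1.1.1, 9.1.2, 13.4.1.3, 13.7, 13.7.1 and 13.7.1.1. Section 5.1 allows up to 3.5 hours after treatment; 9.1.1 says three.
2. **Test.** In 13.7.1.2.3 and 13.7.2.2, replace the log-rank test with a paired analysis of percentage change, two-sided 5% with a 95% CI, with success only if p ≤ 0.05 and the change is an improvement. Use one summary per participant over one stated window, after reconciling 21 days (6.2, 8.10) with the one-month treatment period in 12.3. If an event or composite-success endpoint is kept, use an exact one-sample test against a justified, pre-stated reference. State that an uncontrolled before/after change cannot by itself be attributed to the device.
3. **Missing data.** For the paired analysis, replace the censoring rule in 13.7.1.2.1. Analyse participants with at least one complete pair, say that this is not the full ITT set of 13.4.1.2, and report how many are excluded. Add a tipping-point analysis with progressively unfavourable changes for those missing.
4. **Secondaries.** Name and order the two in 13.7.1.2.4. No events follow the heading of 13.7.2.1 in the text available.
5. **Subgroups.** Drop the treatment and interaction terms from 13.7.1.2.5.
6. **Events.** If the paired endpoint is chosen, report the 13.7.1.1 events as safety outcomes with an exact 95% CI, and reconcile the Clinical Events Committee text (6.4, Appendix 4) and the waiver in 10.3.
7. **Looks.** State that those in 6.3 are for safety only and carry no efficacy test.
8. **Sample size.** In 13.2, state what 70 delivers for the paired test (0.34 SD at 80% power, 0.39 SD at 90%, half-width 0.24 SD) beside the figures for 63 (0.36, 0.41 and 0.25 SD), since withdrawals are not replaced.
9. **SAP.** State the same rule there.

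The cost is a protocol amendment and SAP text, with no extra participants. Section 26 requires IRB/EC approval of amendments while 15.4 says that an IRB/EC is not required; these must be reconciled.

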#### **13.7.1.2.4 Multiple Comparisons/Multiplicity**

If the primary efficacy reaches statistical significance, then the two secondary endpoints will be formally tested at the 5% level in a hierarchical (step-down) procedure.

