## **5.2 Secondary Objective**

To observe the quality of lung function that participants experience during the use of the device during the trial period.

Outcome measured by:

Percentage change of lung function. Evaluate expiratory forced vital capacity (FVC) and forced expiratory volume (FEV1) will be monitored with standard spirometer. Change from baseline before treatment and measure again up to 3.5 hours after treatment.

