#### **9.1.1.2 Secondary Criterion**

Percent change of spirometer reading from before treatment compared to three (3) hours after treatment by the participant. Subjective participant opinion of the efficacy provided by semi-weekly surveys.

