#### **13.4.1.3 General Statistical Approach**

All statistical tests will be two-sided.

All summary tables for quantitative parameters will display mean, standard deviation, median, range (minimum and maximum), as well as number of missing data (if relevant). All summary tables for qualitative parameters will display counts, percentages and number of missing data if relevant.

Baseline data are defined as the last measurement performed before the first study medical device intake.

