### **13.7.2 Secondary/Other Efficacy Variables**

#### **13.7.2.1 Description of Secondary/Other Variables**

Secondary endpoint: The composite cluster of the first occurrence, over the duration of study (randomization to study end date inclusive), of the following cluster of events:

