Statistical and Analytical Plan:

All study practices and statistical methods are based on the International Conference on Harmonization (ICH) document "Statistical Principles for Clinical Trials."

Data will be summarized by treatment group. Baseline characteristics, and safety outputs total overall columns will be included to summarize all subjects.

For all baseline, demographic, safety and efficacy outputs data will be summarized by treatment group.

In summary tables of continuous variables, the minimum and maximum statistics, the arithmetic mean and median, the 95% confidence interval, standard deviation, and standard error will be presented will to the same number of decimal places as the original data.

In summary tables of categorical variables, counts and percentages will be used. The denominator for each percentage will be the number of subjects within the population treatment group unless otherwise specified.

All hypothesis testing will be carried out at the 5% (2-sided) significance level unless otherwise specified.

P-values will be rounded to three decimal places. P-values less than 0.001 will be reported as <0.001 in tables.

At the conclusion of the trial, the raw data shall be analyzed by a blinded statistician of Mack Biotech, Corp. and then create a report with the clinical trial outcome.

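### The step-down test of two secondary endpoints has no fixed members or order, so family-wise control at 5% is not assured

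*Protocol*

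**What the plan says.** Section 13.7.1.2.4 sets a gate, "If the primary efficacy reaches statistical significance", and then states that "then the two secondary endpoints will be formally tested at the 5% level in a hierarchical (step-down) procedure". It neither names the two endpoints nor orders them.

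The places where they could be identified are these:

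- Section 5.2 gives two lung-function measures, as percentage change up to 3.5 hours after treatment: "Evaluate expiratory forced vital capacity (FVC) and forced expiratory volume (FEV1) will be monitored with standard spirometer".
- Section 9.1.1.2 gives percentage change in an unspecified spirometer reading at 3 hours, and also "Subjective participant opinion of the efficacy provided by semi-weekly surveys".
- Section 9.1.2 lists only the surveys as secondary and puts spirometry under primary. Section 9.1.1 also lists spirometry as primary.
- Section 13.7.2.1 gives a single secondary endpoint of a different kind: "The composite cluster of the first occurrence, over the duration of study (randomization to study end date inclusive), of the following cluster of events". No component events follow in the text available.

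Section 13.7.2.2 analyses the secondaries by the primary's method, "except for weight and waist circumference". Section 13.7.1.2.3 gives that method as Kaplan-Meier curves with a two-sided log-rank test. Section 13.4.1.3 adds "All statistical tests will be two-sided". The SAP names no secondary endpoint, order or multiplicity rule and says "All hypothesis testing will be carried out at the 5% (2-sided) significance level unless otherwise specified". Section 13.1 promises a final plan before data lock, with revisions made on blinded review.

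**The concern.** Testing in sequence, each step at the full 5%, controls the family-wise error only when the members and their order are set before results are known. Here a reader cannot tell whether the two are FVC and FEV1, a spirometer reading and the survey, or something that includes the event composite. If the choice is made late, FEV1, FVC or the survey could be presented as the formally tested secondary, whichever looks best.

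The analysis method is also mismatched. A log-rank test does not analyse a before/after change in spirometry, and a single arm offers no second curve to compare. The exception for weight and waist circumference concerns two variables that no section names as endpoints, so it does not help to identify the intended pair.

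**Working it through.** **Inputs.** Level 0.05 per step, two-sided (13.7.1.2.4, 13.4.1.3, SAP). Gate: significant primary (13.7.1.2.4). One arm (8.3). The documents give no correlation between endpoints, no number of candidates beyond the conflicting lists, and no power for the primary. Those values below are assumptions.

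**Step 1: the sections side by side.**

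| Section | Secondary endpoints | Number |
|---|---|---|
| 13.7.1.2.4 | not named | 2 |
| 5.2 | FVC, FEV1 | 2 |
| 9.1.1.2 | spirometer reading, survey opinion | 2 |
| 9.1.2 | survey only | 1 |
| 13.7.2.1 | event composite | 1 |

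Two lists have the right count but different members. The other two have the wrong count. None gives a testing order.

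**Step 2: reproduce the stated 5%.** With members and order fixed and both nulls true, a false claim requires rejecting the first null, so the error is 0.05. The plan's figure is right for a fixed sequence.

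**Step 3: members or order chosen after the results, gate passed, all k candidates null and independent.** Error = 1 − 0.95^k.

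- k = 2: 1 − 0.9025 = 0.0975
- k = 3: 1 − 0.857375 = 0.1426

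**Step 4: allow for correlation (assumed).** For two candidates, error = 1 − P(|Z1| ≤ 1.96 and |Z2| ≤ 1.96) under a bivariate normal.

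- correlation 0.5: 9.1%
- correlation 0.8: 7.8%
- correlation 0.9: 7.0%

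For three candidates with FEV1 and FVC correlated and the survey independent, error = 1 − 0.95 × (1 − two-candidate error).

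- correlation 0.8: 1 − 0.95 × 0.922 = 12.4%
- correlation 0.9: 1 − 0.95 × 0.930 = 11.7%

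**Step 5: allow for the gate.** Multiply by the chance that the gate opens, taking the primary as independent of the secondaries.

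- Primary effect real with assumed power 80%, k = 2: 0.80 × 0.0975 = 7.8%.
- Primary null and its test valid, k = 2: 0.05 × 0.0975 = 0.5% for a false secondary claim. The overall error stays at 5%, because any error must begin with a false primary result.

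Inflation above 5% therefore needs a passed gate, null secondaries and a choice that follows the data.

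**Step 6: can the gate be computed?** Section 13.7.1.2.3 needs a two-sided log-rank test. Section 8.3 puts every participant in one arm, and no reference curve is given. As written the test cannot be run, so the step-down cannot start. The figures above apply only once the gate has been repaired.

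**The case against.** The strongest reply is that 13.7.1.2.4 does contain a gate and a hierarchy, and that 13.1 makes section 13 only the basis for a later plan. If that plan fixes two members and an order before anyone sees results, the error is 5% and nothing is lost. This stands in principle. The protection is limited, though. A blinded review conceals allocation, and a single arm has none to conceal: whoever sees the pooled before/after data sees the result. The SAP supplied does not close the gap.

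Step-down could also mean Holm's procedure, which needs no fixed order. It still needs fixed members, and with two tests it starts at 0.05/2 = 2.5%, which does not match the stated 5% for each test.

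Three stronger readings are tempting, and the documents do not support them:

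- A reader might infer that the SAP overrides the hierarchy by testing everything at 5%. Its rule yields to other specifications, and a fixed sequence also tests each step at 5%, so the two are compatible.
- A reader might infer that the exception in 13.7.2.2 names variables foreign to this trial. Section 12.1.2 records weight at baseline. The supportable statement is that neither weight nor waist circumference is named as an endpoint.
- A reader might infer that the composite in 13.7.2.1 was left blank. The list may have been lost when the file was converted to text. The conflict among 5.2, 9.1.1.2 and 9.1.2 stands without it.

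**Conclusion.** The point holds as a failure to define the procedure. Section 13.7.1.2.4 refers to two secondaries that no section identifies consistently and none orders, and 13.7.2.2 gives them a method that does not fit the spirometry measures. Family-wise control at 5% is not assured.

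A reader might go further and infer that the 5% level is already broken. The documents do not show that. They give 5% as the level of the tests and state no separate family-wise figure, and any members and order fixed beforehand would hold it.

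The size is an upper figure under the conditions in Step 5: 9.75% for two independent candidates and 14.3% for three, with lower values under correlation or with an uncertain gate. The correlations, the number of candidates and the gate power are assumptions. The finding that members and order are undefined rests on the text alone.

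**What to change.** Before any data are reviewed:

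1. As a precondition, replace the log-rank gate with one primary endpoint and one test that can be computed in a single arm. The primary itself now differs between 5.1 (oxygen saturation change), 9.1.1.1 (a success composite) and 13.7.1.1 (an adverse-event-type composite).
2. In 13.7.1.2.4 and the SAP, name exactly two secondaries in one fixed order. FEV1 change then FVC change would use the measures already in 5.2; the sponsor may choose the reverse order.
3. Give them one time point, reconciling 3 hours in 9.1.1.2 with up to 3.5 hours in 5.2.
4. Analyse each as a paired before/after change at two-sided 5%. Test the first only if the primary is significant, and the second only if the first is significant.
5. Report the survey descriptively with a confidence interval.
6. Align 5.2, 9.1.1, 9.1.1.2, 9.1.2, 13.7.2.1 and 13.7.2.2 so that spirometry sits in one tier only. Remove the weight and waist clause. Remove the composite in 13.7.2.1 if the original document confirms that its list is empty.

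For the secondaries the cost is protocol and SAP wording, using measures already planned. The downside is that the second endpoint carries no formal claim if the first is not significant, and the survey carries none at all.
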